### 9.2.4 Prior and Concomitant Medications

Medications will be coded using the World Health Organization Drug Dictionary (WHO-DD) and categorized as follows:

**Prior medication:** any medication that was administered during the 56 days before the first dose of study drug, regardless of when it ended.

**Concomitant medication:** medication continued or newly received on or after the first dose date of study drug through the end of the TE period.

**Post-treatment medication:** medication continued or newly received after the TE period.

A given medication may be classified as follows: prior, concomitant, post-treatment, both prior and concomitant, both concomitant and post-treatment, or prior, concomitant, and post-treatment.

If a medication has a completely missing or partially missing start/stop date and it cannot be determined whether it was taken before the first dose date of study drug, concomitantly during

the TE period, or after the TE period, it will be classified as prior, concomitant, and post-treatment.

For the FAS, prior medications and concomitant medications will be summarized descriptively by: 1) treatment group and overall, preferred name (PN); and 2) treatment group and overall, anatomic class (ATC) level 1, ATC level 2, and PN. Post-treatment medications will be listed for each subject.

Details for imputing missing or partial start and/or stop dates of medication are described in [Appendix B](#).

### **9.2.5 Study Drug Exposure**

Duration of study drug exposure (in days) will be calculated as: last dose date of study drug – first dose date of study drug + 1, regardless of study drug interruption, and will be summarized descriptively.

Study drug exposure (in weeks) will be summarized descriptively by the number of subjects (n), mean, SD, median, min, and max. It will also be summarized in categories for Treatment Period:  $\leq 1$  week,  $>1-\leq 2$  weeks,  $>2-\leq 4$  weeks,  $>4-\leq 8$  weeks,  $>8-\leq 12$  weeks,  $>12-\leq 16$  weeks,  $>16-\leq 20$  weeks,  $>20-\leq 24$  weeks, and  $>24$  weeks, using counts and percentages. Additionally, the total study drug exposure, defined as the sum total of the study drug exposure across all subjects (in patient-weeks and patient-years), will be provided.

Exposure summaries will be based on the Safety Set, and presented by treatment group and overall.

### **9.2.6 Study Drug Compliance**

Study drug compliance will be calculated as:  $100 \times [1 - (\text{total number of days of study drug interruption}) / (\text{duration of study drug exposure in days})]$ . A study drug interruption on a given day is defined as an interruption of any study drug on that day. A study drug interruption that continues through the end of the study participation (i.e., subject does not resume study drug before the end of the study participation) will not be included in the compliance calculation.

Percentage of study drug compliance will be summarized based on the FAS, and presented by treatment group and overall. Percentage of study drug compliance will be summarized descriptively by the number of subjects (n), mean, SD, median, min, and max. It will also be summarized in categories:  $<80\%$  and  $\geq 80\%$  using frequency tables.

In addition, percentage of tablets taken will be calculated using the following formula:

$100 \times [(\text{total number of tablets dispensed}) - (\text{total number of tablets returned})] / (\text{total number of tablets planned to be taken per day} \times \text{duration of study drug exposure in days})$ . Summary similar to those for the study drug compliance will be produced based on the FAS.

### **9.2.7 Important Protocol Deviations**

An important protocol deviation (IPD) is a deviation that may significantly affect the completeness, accuracy, or reliability of the study data or that may significantly affect a subject's rights, safety, or well-being. IPD rules will be developed and finalized prior to the IA data lock.

The protocol deviations that should be considered as potential IPDs include, but are not limited to:

- Subject was enrolled in the study despite the violation of inclusion/exclusion criteria
- Subject was less than 80% compliant with study drug for non-safety reason
- Subject received prohibited concomitant medications
- Subject received the wrong treatment or incorrect doses
- Subject remained in the study despite meeting withdrawal criteria

Occurrence of any of these events should be considered as potential IPDs, but a blinded team should categorize them as IPDs only if they have the potential to significantly affect the completeness, accuracy, or reliability of the study data or that may significantly affect a subject's rights, safety, or well-being.

IPDs (from the clinical database or from the site deviation log) will be summarized descriptively based on the FAS and presented by treatment group and overall. Additionally, IPDs will be provided in an individual subject data listing.

### **9.3 Efficacy Analysis**

All efficacy analyses described in this section will be based on the FAS, unless otherwise specified.

#### **9.3.1 Analysis of Primary Efficacy Variable**

##### **9.3.1.1 Definition of Variables**

The primary efficacy variable is the absolute change in ppFEV1 from baseline at Week 4. Percent predicted FEV1 is the ratio of FEV1 (L) and predicted FEV1 (L), expressed as a percentage. See [Appendix C](#) for more details.

##### **9.3.1.2 Primary Analysis**

The primary analysis will be performed using a mixed-effects model for repeated measures (MMRM) with change from baseline at Day 15, Week 4, Week 8, Week 12, Week 16, and Week 24 as the dependent variable. The model will include treatment group, visit, and treatment by visit interaction as fixed effects, with continuous baseline ppFEV1, age at screening (<18 versus ≥18 years of age) and sex (male versus female) as covariates. The model will be estimated using restricted maximum likelihood. Denominator degrees of freedom for the *F*-test for fixed effects will be estimated using the Kenward-Roger approximation. An unstructured covariance structure will be used to model the within-subject errors. If the model estimation does not converge, a compound symmetry covariance structure will be used instead. Conditional on the observed data and covariates, missing data will be assumed to be missing at random; consequently, no imputation of missing data will be performed.

The primary result obtained from the model will be the estimated treatment difference at Week 4. The adjusted means with 2-sided 95% confidence intervals and 2-sided *P* values will be provided. Furthermore, the treatment difference at each post-baseline visit obtained from the model will also be provided.

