## **9.2 Method of Assigning Subjects to Treatment Groups**

Subjects will be randomized (1:1) to the TC VX-659/TEZ/IVA arm or to the triple placebo arm. Randomization will be stratified by ppFEV1 determined during the Screening Period (<70 versus ≥70), age at the Screening Visit (<18 versus ≥18 years of age), and sex (male versus female).

An interactive web response system (IWRS) will be used to assign subjects to treatment. The randomization code list will be produced by Vertex Biometrics or a qualified randomization vendor.

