## **11.6 Efficacy**

### **11.6.1 Spirometry**

Spirometry will be performed according to the American Thoracic Society Guidelines/European Respiratory Society Guidelines and according to the additional guidelines that follow.

Pre-bronchodilator spirometry is defined as spirometry testing performed for subjects who have

- withheld their short-acting bronchodilators (e.g., albuterol) or anticholinergic (e.g., ipratropium bromide [Atrovent®]) for more than 4 hours before the spirometry assessment;
- withheld their long-acting bronchodilator (e.g., salmeterol) for more than 12 hours before the spirometry assessment; and
- withheld their once-daily, long-acting bronchodilator (e.g., tiotropium bromide [Spiriva®]) for more than 24 hours before the spirometry assessment.

During the Screening Period, spirometry assessments may be performed pre- or post-bronchodilator. At all other visits, all spirometry assessments should be performed pre-bronchodilator. During the Treatment Period, spirometry assessments must be performed before study drug dosing ([Section 9.6.1](#)) at approximately the same time at each visit. In the event that a subject forgets to withhold bronchodilator(s), spirometry should be performed according to the following:

[figure not shown]
- If a subject's Day 1 spirometry assessment is pre-bronchodilator, but, on a subsequent visit, the subject forgets to withhold bronchodilator use, a post-bronchodilator spirometry assessment will be obtained for that visit only, and the visit will not be rescheduled.
- If, on Day 1, the subject forgets to withhold his/her dose of bronchodilator, spirometry should be performed post-bronchodilator, and all subsequent spirometric measurements (according to the schedule of assessments in [Table 3-2](#)) should be performed post-bronchodilator.
- Each spirometry assessment will be recorded in the source documents as pre- or post-bronchodilator.

All sites will be provided with spirometers to be used for all study assessments. Spirometry data will be transmitted to a centralized spirometry service for quality review. The investigator's assessment of the spirometry results will be used for the screening assessment and determination of eligibility.

See [Section 10.7.1](#) for information about access to spirometry results.

The measured spirometric values listed below will be converted to percent predicted values using the standard equations of GLL.

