## **7.3 Randomization**

Subjects will be randomized (1:1) to the VX-659/TEZ/IVA arm or to the triple placebo arm. Randomization will be stratified by ppFEV1 determined during the Screening Period (<70 versus  $\geq 70$ ), age at the Screening Visit (<18 versus  $\geq 18$  years of age), and sex (male versus female).

An interactive web response system (IWRS) will be used to assign subjects to treatment. The randomization code list will be produced by Vertex Biometrics or a qualified randomization vendor.

Randomization will occur before the first dose of study drug during the Treatment Period and may occur on either Day 1 or Day -1.

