### 9.3.2.2 Analysis Method

Absolute change in ppFEV1 through Week 24: Analysis of this variable will be based on an MMRM that is exactly the same as the primary efficacy variable. However, the Day 15 Visit will not be included in the estimation of the average treatment effect through Week 24 as the treatment effect is not expected to reach the steady state at Day 15.

Number of PEx through Week 24: Analysis of this variable will be performed using a negative binomial regression model with a fixed effect for treatment, as well as continuous baseline ppFEV1, age at screening (<18 versus ≥18 years of age), and sex (male versus female) as covariates. The logarithm of the subject-specific PEx analysis period duration (in years) will be treated as the offset in the model.

Absolute change in SwCl from baseline through Week 24: Analysis of this PD variable will be based on an MMRM similar to the analysis of the primary efficacy variable. Data obtained from Week 4, Week 8, Week 12, and Week 24 Visits will be included in the model and all of these visits will be included in the estimation of the average treatment effect through Week 24.

Absolute change in the CFQ-R respiratory domain score from baseline through Week 24: Analysis of this domain will be based on an MMRM similar to the analysis of the primary efficacy variable. Data obtained from Week 4, Week 8, Week 12, Week 16, and Week 24 Visits will be included in the model and all of these visits will be included in the estimation of the average treatment effect through Week 24.

Absolute change in BMI from baseline at Week 24: Analysis of this variable will be based on an MMRM similar to the analysis of the primary efficacy variable. Data obtained from Day 15, Week 4, Week 8, Week 12, Week 16, and Week 24 Visits will be included in the model.

Absolute change in SwCl from baseline at Week 4: Analysis of this PD variable will be based on an MMRM similar to the analysis of the primary efficacy variable. Data obtained from Week 4, Week 8, Week 12, and Week 24 Visits will be included in the model to estimate the treatment effect at Week 4.

Absolute change in CFQ-R respiratory domain score from baseline at Week 4: Analysis of this domain will be based on an MMRM similar to the analysis of the primary efficacy variable.

Data obtained from Week 4, Week 8, Week 12, Week 16 and Week 24 Visits will be included in the model to estimate the treatment effect at Week 4.

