### 9.3.3.2 Analysis Method

Time-to-first PEx through Week 24: Time-to-first PEx will be analyzed using the Cox regression model. The model will include a fixed effect for treatment, as well as continuous baseline ppFEV1, age at screening (<18 versus ≥18 years of age), and sex (male versus female) as covariates. Additionally, the Kaplan-Meier method will be used to produce a graphical presentation of the cumulative exacerbation-free rate for each treatment group and to estimate the cumulative exacerbation-free rate by treatment group.

[figure not shown]
Note: If the number of events is <5 in either treatment group, Cox regression will not be performed and the analysis of the time-to-first event will be restricted to the Kaplan-Meier method.

Absolute change in BMI z-score from baseline at Week 24 (for subjects ≤20 years of age at Baseline): Analysis of this variable will be based on an MMRM similar to the analysis of the primary efficacy variable, excluding the covariate of age at screening (<18 versus ≥18 years of age), for subjects ≤20 years of age at Baseline. Data obtained from Day 15, Week 4, Week 8, Week 12, Week 16, and Week 24 Visits will be included in the model.

Absolute change in body weight from baseline at Week 24: Analysis of this variable will be based on an MMRM similar to the analysis of the primary efficacy variable. Data obtained from Day 15, Week 4, Week 8, Week 12, Week 16, and Week 24 Visits will be included in the model.

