##### **10.1.3.1 Analysis of Primary Efficacy Variable**

The analysis of the primary efficacy variable of absolute change in ppFEV1 from baseline at Week 4 will be performed using an MMRM with change from baseline at Day 15 and Week 4 as

the dependent variable. The model will include treatment group, visit, and treatment by visit interaction as fixed effects, with continuous baseline ppFEV1, age at screening (<18 versus ≥18 years of age) and sex (male versus female) as covariates. The model will be estimated using restricted maximum likelihood. Denominator degrees of freedom for the *F*-test for fixed effects will be estimated using the Kenward-Roger approximation. An unstructured covariance structure will be used to model the within-subject errors. If the model estimation does not converge, a compound symmetry covariance structure will be used instead. Conditional on the observed data and covariates, missing data will be assumed to be missing at random; consequently, no imputation of missing data will be performed.

[REDACTED]

[REDACTED]

- [REDACTED]
- [REDACTED]
- [REDACTED]
- [REDACTED]

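### Randomization is stratified by screening ppFEV1, but the visible ppFEV1 models use neither the stratum nor the screening value, so their intervals may be somewhat wider than the collected data allow (low priority)

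*SAP*

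**What the plan says.** SAP 7.3 states: "Randomization will be stratified by ppFEV 1 determined during the Screening Period", with the cut at 70, together with age group and sex. Protocol 9.2 says the same.

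The primary MMRM (SAP 9.3.1.2, matching Protocol 12.3.3.1.1) is fitted with continuous baseline ppFEV1, "age at screening (<18 versus ≥18 years of age) and sex (male versus female) as covariates". The interim MMRM in SAP 10.1.3.1 has the same covariates. For ppFEV1 through Week 24, SAP 9.3.2.2 says: "Analysis of this variable will be based on an MMRM that is exactly the same as the primary efficacy variable". The negative binomial, Cox and interim ANCOVA models also list baseline ppFEV1, age group and sex. The below-70 stratum appears only as a descriptive category in SAP 9.2.2.

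Baseline is the last available reading before first dose (SAP 9.1). Spirometry is scheduled at screening and on Day 1 (Protocol Tables 3-1 and 3-2), so baseline is normally the Day 1 value. The two readings need not be taken under the same conditions. Protocol 11.6.1 says: "During the Screening Period, spirometry assessments may be performed pre- or post-bronchodilator".

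**The concern.** It is usual to adjust for the factors used in stratified randomization, and one of the three is missing here. Continuous baseline ppFEV1 carries most of the same prognostic information but not necessarily all of it. Screening and Day 1 are separate, imperfect readings of the same lung function. If the Day 1 reading contains noise that the screening reading does not share, the screening value helps predict the Week 4 value even after Day 1 is known.

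What is at stake is the interval width for the Week 4 difference (interim and final) and for the through-Week-24 difference. It matters most at the interim, where about 140 subjects may support a regulatory submission.

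**Working it through.** **1. The plan's own power figures.** Inputs from SAP 7.2: SD 7, difference 5.0, 70 per arm with 5% dropout at the interim (70 × 0.95 = 66.5), two-sided alpha 0.044.

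- Interim: SE = 7 × √(2/66.5) = 1.214; 5/1.214 = 4.119; 4.119 − 2.014 = 2.105; power 98.2% (98.1% with the t distribution). Stated: about 98%.
- Final: 180 × 0.90 = 162 per arm, alpha 0.01. SE = 7 × √(2/162) = 0.778; 5/0.778 = 6.43; 6.43 − 2.58 = 3.85; power above 99.9%. Stated: about 99%.

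The stated figures are met, so the question is only about unused precision.

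**2. Model for the gain.** Screening S = T + e_S, Day 1 B = T + e_B, Week 4 Y = T + Δ + e_Y, scaled so that Var(Y − B) = 7² = 49. The SD of 7 is the only input from the documents. Assumed: between-subject SD of T 11 to 14, visit-noise SD 2.2 to 4.95. Compare Var(Y given B) with Var(Y given B and S).

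**3. Independent noise, example with between-subject SD 14 and visit SD 4.**

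- Var(Δ) = 49 − 2 × 16 = 17.
- Var(T given B) = 1/(1/196 + 1/16) = 14.79; Var(T given B, S) = 1/(1/196 + 2/16) = 7.69.
- Residual variance goes from 14.79 + 17 + 16 = 47.79 to 7.69 + 33 = 40.69, a cut of 14.9% (SD 6.91 to 6.38).

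**4. Serially correlated noise, same example.** Assume correlation ρ per 28 days, with screening 21 days before Day 1 and Week 4 28 days after it. At ρ = 0.3:

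- Var(Δ) = 49 − 32 × 0.7 = 26.6, so Var(Y) = 196 + 26.6 + 16 = 238.6.
- Cov(B,Y) = 196 + 16 × 0.3 = 200.8; Cov(S,B) = 196 + 16 × 0.3^0.75 = 202.49; Cov(S,Y) = 196 + 16 × 0.3^1.75 = 197.95.
- Var(Y given B) = 238.6 − 200.8²/212 = 48.41.
- S removes a further (197.95 − 202.49 × 200.8/212)² / (212 − 202.49²/212) = 6.157²/18.60 = 2.04.
- Cut: 2.04/48.41 = 4.2%.

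**5. Range (between-subject SD 14).** Percentage cut in Week 4 residual variance from adding continuous screening ppFEV1. The second data column adds an extra SD of 4 to the screening reading, to represent mixed bronchodilator state. The correlated columns have no such extra noise.

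| Visit SD | Independent | Independent, extra screening SD 4 | ρ = 0.3 | ρ = 0.5 | ρ = 0.7 |
|---|---|---|---|---|---|
| 2.2 | 4.8 | 1.8 | 1.4 | 0.5 | 0.1 |
| 3 | 8.7 | 4.5 | 2.5 | 0.9 | 0.2 |
| 4 | 14.9 | 9.8 | 4.2 | 1.4 | 0.3 |
| 4.95 | 22.1 | 16.5 | 6.1 | 2.1 | 0.4 |

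At between-subject SD 11 the independent-noise figures are slightly lower (8.3, 14.1 and 20.6 at visit SD 3, 4 and 4.95). The bottom row is a corner case: 2 × 4.95² = 49, so all change variance is noise and subjects do not differ in response.

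**6. The stratum alone.** Simulations with independent noise and screening limited to 40–90 gave a cut of roughly 0.5% to 7%. With 171 per arm (180 × 0.95) and visit SD 4, the Week 4 standard error was 0.744 as planned, 0.731 with the stratum and 0.691 with continuous screening ppFEV1.

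**7. What this does to the intervals.** Taking the current residual SD as 7, the 95% half-width at the interim is 1.96 × 1.214 = 2.38 points. A 2% cut gives 2.38 × √0.98 = 2.36, 6% gives 2.31 and 22% gives 2.10. At the final analysis (162 per arm), 1.52 becomes 1.48 at 6% and 1.35 at 22%.

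**The case against.** The case for leaving the model alone is strong. Protocol and SAP agree with each other, and the omission does not bias the estimate; at most the model standard error is slightly conservative. Continuous Day 1 ppFEV1 is the better single covariate.

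Screening is also not simply a repeat of Day 1:

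- It may be post-bronchodilator, and eligibility rests on the investigator's assessment of it (Protocol 11.6.1).
- It may be repeated once to establish eligibility (9.1.1.1).
- Its window may be extended by 2 weeks, including for a modulator washout (9.1.1.3).
- Day 1, but not screening, is synchronised with inhaled-antibiotic cycles (9.5).

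Since screening is further from Week 4 than Day 1 is, serial correlation can remove almost all of the gain. All of this stands, and it is why the range reaches down to about zero. It does not show that the extra covariate does harm.

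Four stronger readings are tempting but not supported:

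- **Day 1 noise passes straight into the endpoint because change subtracts it.** Baseline is a covariate. Modelling Y − B with βB is the same as modelling Y with (β + 1)B, and the treatment estimate is identical. The noise only makes the covariate imperfect.
- **The variance cut amounts to free extra subjects.** Sample size was set by pulmonary exacerbations (Protocol 12.1), and ppFEV1 power is already 98% or more.
- **The BMI z-score model wrongly drops the age stratum.** SAP 9.3.3.2 does fit it "excluding the covariate of age at screening (<18 versus ≥18 years of age"), but the score is already age-adjusted, the subset is 20 years or younger, and the protocol asks only for a similar model.
- **No model anywhere uses the screening value.** Text next to both primary-model sections is redacted, so this can be said only of the visible models.

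**Conclusion.** The point holds as a modest, low-priority improvement. The visible primary, interim and through-Week-24 ppFEV1 models leave out one of the three stratification factors and a second pre-dose reading. There is no bias and no power shortfall.

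The gain from continuous screening ppFEV1 at Week 4 is about 2% to 22% of residual variance if visit noise is independent. The low end combines visit SD 2.2 with extra screening noise; the high end assumes no variation in response. With serial correlation of 0.3 to 0.7 per 28 days the gain is about 0% to 6%. In interval terms this is at most about 0.3 point off a half-width of 2.4 at the interim, against a planned difference of 5 points, and often far less. Between-subject SD, visit noise and serial correlation are all assumptions; the documents supply only the SD of 7.

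**What to change.** Before interim data lock and unblinding, keep Day 1 as baseline and add one prespecified covariate to SAP 9.3.1.2 and 10.1.3.1 and to Protocol 12.3.3.1.1 and 12.3.3.3.1. This should be the randomized below-70 versus 70-or-above stratum or, preferably, the continuous screening ppFEV1 used for stratification. The through-Week-24 analysis then inherits it.

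Add a pre/post-bronchodilator indicator for screening only if that field is in the analysis database; Protocol 11.6.1 shows it only in source documents.

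The cost is SAP and protocol wording and one or two model degrees of freedom. No new assessment is needed, because screening ppFEV1 is required for eligibility and stratification.

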### **9.3.2.3 Multiplicity Adjustment**

The Lan and DeMets alpha spending function will be applied to the primary endpoint of the absolute change in ppFEV1 at Week 4 to control the overall type I error rate of 0.05 such that an alpha of 0.01 will be preserved for the final analysis.

If the number of subjects included in the IA is 140, the primary endpoint of the absolute change from baseline in ppFEV1 at Week 4 will be tested at an alpha of 0.044 during the IA. The actual alpha at the IA ( $\alpha_0$ ) will be determined based on the actual number of subjects included in the interim Full Analysis Set. If the study does not cross the efficacy boundary during the IA (*P* value  $\geq \alpha_0$ ), then the primary endpoint will be tested at an alpha of 0.01 at the final analysis when all subjects complete the study participation. See Section 7.5 for more details.

The key secondary endpoints will be formally tested at an alpha of 0.05 at the final analysis when all subjects complete study participation only if the primary endpoint is statistically significant at the IA or at the final analysis. A hierarchical testing procedure will be used to control the type I error rate for the multiple key secondary endpoints tested at an alpha of 0.05. For a test at any step to be considered statistically significant within the testing hierarchy, it must be statistically significant, and all previous tests (if any) within the hierarchy must be statistically significant at the 0.05 level. The testing order of the key secondary endpoints is as follows:

- Absolute change in ppFEV1 from baseline through Week 24
- Number of PEx through Week 24
- Absolute change in SwCl from baseline through Week 24
- Absolute change in CFQ-R respiratory domain from baseline through Week 24
- Absolute change in BMI from baseline at Week 24
- Absolute change in SwCl from baseline at Week 4
- Absolute change in CFQ-R respiratory domain score from baseline at Week 4

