## **5.2 Efficacy Analysis**

### **5.2.1 Analysis of Endpoints Based on the Number of Clinical Events**

Number of Pulmonary Exacerbation (PEX) through Week 24: The analysis pre-specified in the protocol based on the negative binomial regression model will be performed first. If the negative binomial regression does not converge, the analysis will be performed using the Poisson regression with the same covariates and offset.

Note: If the number of events is less than 5 in either treatment group, neither the negative binomial regression nor the Poisson regression will be performed and analysis of event counts will be based on a Fisher's Exact test.

Analysis of the number of PEX requiring hospitalization and/or IV antibiotics therapy, the number of planned hospitalizations for CF, and the number of unplanned hospitalizations for reasons other than antibiotic therapy for sinopulmonary signs/symptoms will be performed in the same manner.

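### If the unstructured repeated-measures model fails to converge, the plan drops straight to one common variance for all visits; trying heterogeneous structures first is a cheap, low-priority improvement

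*SAP*

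**What the plan says.** SAP 9.3.1.2 models "change from baseline at Day 15, Week 4, Week 8, Week 12, Week 16, and Week 24 as the dependent variable". The fit is by restricted maximum likelihood with Kenward-Roger degrees of freedom. On covariance it says "An unstructured covariance structure will be used to model the within-subject errors", and then "If the model estimation does not converge, a compound symmetry covariance structure will be used instead". Protocol 12.3.3.1.1 gives the same rule. The visible text names no structure between the two and no robust variance.

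SAP 9.3.2.2 makes the model for ppFEV1 through Week 24 identical to the primary model, with one difference in what is read from it: "the Day 15 Visit will not be included in the estimation of the average treatment effect through Week 24". For BMI at Week 24 it says "Analysis of this variable will be based on an MMRM similar to the analysis of the primary efficacy variable", and it words the sweat chloride and CFQ-R models in nearly the same way. The natural reading is that all of them inherit the fallback.

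For the interim analysis (IA), SAP 10.1.3.1 fits the model "using an MMRM with change from baseline at Day 15 and Week 4 as" the dependent variable, with the same fallback. Protocol 12.3.3.3.1 takes the remaining details of the IA model from the final-analysis section.

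**The concern.** Six visits give 6 × 7 / 2 = 21 unstructured covariance parameters. Compound symmetry has two: one variance and one covariance. The quantities tested are visit-specific (ppFEV1 at Week 4, BMI at Week 24) or an average that omits one modelled visit (ppFEV1 through Week 24). Compound symmetry replaces each visit's variance by the mean over visits, so a visit whose variance is above that mean gets too small a standard error, and one below it too large.

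These tests are confirmatory. In SAP 9.3.2.3 ppFEV1 through Week 24 is the first key secondary and BMI at Week 24 the fifth, with two tests behind it, and "all previous tests (if any) within the hierarchy must be statistically significant at the 0.05 level". If the fallback ran, a step could pass on an understated standard error, or fail on an overstated one. The purpose of a prespecified fallback is to keep the test valid when the preferred model cannot be fitted. This one does so only if visit variances are about equal, which the documents do not state.

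**Working it through.** **The plan's own figures.** SAP 7.2 gives SD 7, difference 5.0, 70 per arm at the IA with 5% dropout (66.5 per arm) and 2-sided alpha 0.044. Power = Φ(5 / (7√(2/66.5)) − 2.014) = Φ(4.119 − 2.014) = 98.2%; the plan states about 98%. At the final analysis, with 171 per arm (5% dropout) and alpha 0.01: Φ(6.605 − 2.576) > 99.9%; the plan states about 99%. The plan gives no figure for the fallback.

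**Assumptions.** The variance of change is constant, rising or falling over days 14, 28, 56, 84, 112 and 168. Three between-visit correlations are used: exchangeable 0.6; 0.8 per visit step, decaying; and 0.4 + 0.4 × 0.7^lag. Data are complete.

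**Single visit.** The estimate is the usual difference in means, but its model SE uses the mean variance. So

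SE ratio r = √(mean visit variance / variance at that visit), and actual error = 2[1 − Φ(z × r)].

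Example, variance growing with the square root of time, Week 4 set to 1: the variances are 0.707, 1, 1.414, 1.732, 2 and 2.449, with mean 1.5505. At Week 24, r = √(1.5505/2.449) = 0.796 and the error is 2[1 − Φ(1.96 × 0.796)] = 11.9%. At Week 4, r = √1.5505 = 1.245 and the error is 2[1 − Φ(2.576 × 1.245)] = 0.13%.

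**Average of the five visits from Week 4 to Week 24.** Same example, exchangeable correlation: the mean covariance over the six visits is 0.8872, so compound symmetry gives (1.5505 + 4 × 0.8872)/5 = 1.0199. The true variance is [8.595 + 0.6 × (6.4845² − 8.595)]/25 = 1.1467, where 8.595 and 6.4845 are the sums of the five variances and five SDs. Then r = √(1.0199/1.1467) = 0.943 and the error is 6.5%.

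| Assumed variance of change (Week 24 : Week 4 SD) | BMI at Week 24, nominal 5% | ppFEV1 through Week 24, nominal 5% | Final Week 4 ppFEV1, nominal 1% |
|---|---|---|---|
| Constant (1.00) | r 1.00; 5.0% | r 0.98–1.00; 5.0–5.5% | r 1.00; 1.0% |
| Rising, mild (1.25) | r 0.884; 8.3% | r 0.95–0.97; 5.8–6.3% | r 1.10; 0.44% |
| Rising, square root of time (1.57) | r 0.796; 11.9% | r 0.92–0.94; 6.5–7.0% | r 1.245; 0.13% |
| Falling, 1/square root of time (0.64) | r 1.371; 0.7% | r 1.06–1.09; 3.3–3.7% | r 0.876; 2.4% |

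Ranges in the third column are over the three correlations. A different falling profile (assumed SDs 9, 7, 6, 6, 5.5, 5) gives 1.6% at Week 4. For the planned 5-point effect, Week 4 power stays above 99.9% in every row.

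**Dropout.** With 2% by Day 15 (assumed), 5% by Week 4 and 10% by Week 24, square-root growth gives 12.3–12.6% for Week 24 and 6.8–7.5% for the average.

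**Replacements.** A large-sample calculation with that dropout covered nine settings: constant, square-root and linear growth, each with the three correlations.
- Heterogeneous Toeplitz (11 parameters): 5.0% at Week 24, 1.0% at Week 4, 5.0% for the average.
- Heterogeneous compound symmetry (7 parameters): 4.3–5.0%, 1.00–1.05% and 5.0–5.7%.
- Heterogeneous AR(1): close to nominal at single visits, but 5.0–8.4% for the average.

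A check by 781 simulated trials (180 per arm, square-root growth, third correlation) gave, for Week 24 and the average, 12.6% and 7.2% with compound symmetry, against 4.2% and 5.3% with heterogeneous Toeplitz (Monte Carlo SE 0.7–1.2 points). The falling profile was not run for the replacements.

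**The case against.** The strongest case against is that the rule will probably never run. About 360 subjects support 21 parameters comfortably, and in 6,000 simulated trials (four variance profiles, 1,500 each) the unstructured fit always converged, although by an EM algorithm without covariates, so this is only indicative of the planned fit. The fallback is prespecified, deterministic and the same wherever it appears; nothing is contradictory or ambiguous. Nor is it shown that heterogeneous Toeplitz converges in a data set where unstructured fails. Finally, the primary is most likely decided at the IA, where the change does nothing: with two visits both heterogeneous structures have three parameters and are the unstructured model. All of this stands and sets the priority. It does not make equal variances a sound default for the occasion when the rule does run.

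Three stronger readings are tempting and not supported.
- A reader might infer that the trial's error rate is 8 to 12%. Those figures hold only after non-convergence and under assumed variances.
- A reader might infer that leaving Day 15 out of the average always makes the ppFEV1 through Week 24 test too liberal. It does so with rising variance, or with constant variance and decaying correlation. With constant variance and exchangeable correlation the standard error is exact, and with falling variance it is too large.
- A reader might extend the calculation to variance growing in proportion to time. For ppFEV1 this fits the plan badly: SAP 7.2 uses SD 7 both at Week 4 and for the average, whereas linear growth from 7 implies 7 × √6 = 17.1 at Week 24 and 10.0–10.3 for the average. The mild rising profile implies 6.6–6.8. By the same yardstick the falling profile is also distant (about 4.6–4.7), so it mainly shows the direction of the error.

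**Conclusion.** The point holds as a low-priority robustness gap, not an error or inconsistency. If the six-visit unstructured model did not converge and visit variances differed, the prescribed fallback would misstate standard errors in a direction that cannot be known beforehand. Rising variance makes the Week 24 BMI test clearly liberal, the ppFEV1 average mildly so, and the final Week 4 test conservative; falling variance reverses all three. The sizes rest on assumed variance profiles and correlations, since the only SD in the documents is the planning value of 7. With the planned 5-point effect the primary conclusion would hardly change; what is at stake is the validity of P values and intervals, mainly in the key secondary hierarchy. Redacted entries in the SAP contents between 9.3.1.2 and 9.3.2 may hold sensitivity analyses that cannot be seen, but the fallback sentence itself is fully visible.

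**What to change.** In SAP 9.3.1.2 and Protocol 12.3.3.1.1, replace the fallback sentence with: *If the model with unstructured covariance does not converge, heterogeneous Toeplitz, then heterogeneous compound symmetry, will be used in that order; compound symmetry will be used only if these do not converge.* State that this applies to all final-analysis MMRMs. Heterogeneous AR(1) is left out because it can reach 8.4% for the through-Week-24 average when correlations do not decay.

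Because Protocol 12.3.3.3.1 carries the final-analysis details into the IA, either say that the sequence is for the final analysis only, or put the same sentence in SAP 10.1.3.1. Otherwise the two documents, which now agree, would differ in wording. The IA result is the same either way.

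The cost is a small edit to the protocol and the SAP, a few lines of code, and slightly different intervals if the fallback is ever used.
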